5.2 Response Criteria

- 5.2.1 Methods of Measuring Disease Progression (note: patient's must have non-metastatic disease as an eligibility criteria-see [2.1.1 B Inclusion Criteria](#). New lesions by RECIST Criteria will be for definition of disease progression. Rising serum PSA levels will also be used for determining disease progression-see [5.2.1.3](#) and [5.2.2](#))

All patients in this study must be assessed for response to treatment, even if there are major treatment deviations. Each patient will be assigned one of the following categories: 1) complete response; 2) partial response; 3) stable disease; 4) progressive disease; and 5) not evaluable (early death from malignant disease, early death from toxicity, early death due to other causes, or unknown-not assessable, insufficient data). This protocol will use CTEP's Response Evaluation Criteria on Solid Tumors (RECIST) for assessing response. A quick reference to the RECIST guidelines can be downloaded at the following URL: <http://ctep.cancer.gov/guide>. A copy of this quick reference is found in D.

For patients with declining PSA no restaging will be done unless they develop symptoms consistent with metastatic disease. For patients with rising PSA, once 2 consecutive PSA rises are seen from the last imaging studies, CT and bone scans will be done at their next scheduled visit. (Therefore, restaging scans would be done at an interval no less than 3 months.) They will then be re-staged (CT and bone scans) at 3 month intervals as long as PSA continues to rise.

1. Patients on either arm who develop clinical progression (i.e. evidence of metastatic disease on scans) will be taken off study.
2. Patients who do not develop clinical progression (as defined above), but develop biochemical recurrence (i.e rising serum PSA levels) will undergo the following:
 - Patients randomized to Arm A will have flutamide discontinued and may begin to receive the vaccine as described above following a 4 week delay to determine if there is evidence of an antiandrogen withdrawal response (if they continue to meet the eligibility criteria as outlined in section [2.1](#))
 - Patients randomized to Arm B will have flutamide discontinued, but may continue to receive vaccine treatment.

3. If patients continue to develop biochemical progression following the maneuvers outlined in #2 above, they will come off-treatment, but can remain on study until the development of metastatic disease on scans.

5.2.1.1 CT and MRI are the best currently available and reproducible methods to measure target lesions selected for response assessment. Conventional CT or MRI should be performed with cuts of 10 mm or less in slice thickness contiguously. Spiral CT should be performed using a 5 mm contiguous reconstruction algorithm.

5.2.1.2 Due to the high reported false positive rates of bone scans (30%), patients with a falling PSA (see section 5.2.2.2) with new lesions on bone scan not clinically determined to be related to metastasis (i.e. trauma), and no other evidence of disease progression may remain on trial until the progressive metastatic nature of these lesions has been confirmed on subsequent bone scans.

5.2.1.3 PSA serum levels will be used as a method of measuring disease response or progression. After the initial 3 month evaluation, if a patient has a rising serum PSA level (see section 5.2.2.2) but no evidence of metastatic disease, patients in Arm A will have flutamide discontinued and may begin to receive vaccine alone as described above, since the standard care would be discontinuation of flutamide for rising serum PSA. Those patients who have rising serum PSA levels on Arm B without evidence of metastatic disease will have flutamide discontinued, but may continue to receive vaccine treatment until the development of disease on scans or a second occurrence of rising PSA levels in the absence of clinical progression. If the serum PSA begins or continues to rise off flutamide (Bubley criteria, JCO 1999), vaccine therapy will be discontinued. Since there is no standard of care aside from antiandrogen discontinuation for these patients and they would have already received 2nd line therapy, patients can stay on study until there is evidence of disease on bone scan or CT scan.

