1.1.2 Secondary

Secondary objectives are 1) determining preliminary evidence of any patterns of immunologic effects which differ by treatment including the immunologic effects of flutamide withdrawal on patients continuing on vaccine following a rising PSA on flutamide, 2) estimating toxicity noted on the arms and comparing the results, 3) evaluating, in a preliminary fashion, the effect of vaccine on development of metastatic disease after PSA progression, and 4) evaluating PSA responses and immune responses in patients who have had flutamide stopped at the time of PSA progression and either continue vaccine (Arm B) or have vaccine initiated (arm A) at time of flutamide discontinuation, 5) assessing response rate in patients randomized to both arms, as well as responses in those patients after cross over from the flutamide arm to vaccine only (time of disease progression will be defined as from the first date that vaccine is initiated in those patients who have had flutamide discontinued until the first notation of clinical progression).

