2 ELIGIBILITY ASSESSMENT AND ENROLLMENT

2.1 Eligibility Criteria

2.1.1 Inclusion Criteria

- A. Histopathological documentation of prostate cancer confirmed in the Laboratory of Pathology at the NIH Clinical Center or participating institute's Department of Pathology prior to starting this study. If no pathologic specimen is available, patients may enroll with a pathologist's report showing a histologic diagnosis of prostate cancer and a clinical course consistent with the disease.
- B. Must have non-metastatic androgen insensitive prostate cancer with a rising PSA with castrate levels of testosterone and no evidence of metastatic disease on CT scan or bone scan. A rising PSA is defined as two consecutively rising PSA levels, separated by at least 1 month apart, with the last measurement that is $> 1\text{ng/ml}$. Patients on nilutamide therapy must undergo nilutamide withdrawal for at least 4 weeks and still show evidence of a rising PSA. Following treatment with bicalutamide, patients must undergo withdrawal for at least 6 weeks and still show evidence of a rising PSA.
- C. Life expectancy greater than or equal to 6 months.
- D. ECOG performance status of 0-1.
- E. No systemic steroid or steroid eye drop use within 2 weeks prior to initiation of experimental therapy.
- F. Hematological eligibility parameters (See [APPENDIX C.](#))
 - Granulocyte count $\geq 1,500/\text{mm}^3$
 - Platelet count $\geq 100,000/\text{mm}^3$
 - Hgb $\geq 9\text{ Gm/dL}$
 - Lymphocyte count $\geq 500/\text{mm}^3$.
- G. Biochemical eligibility parameters (within 16 days of starting therapy)
 - Hepatic function: Bilirubin $\leq 1.5\text{ mg/dl}$, OR patients with Gilbert's syndrome, a total bilirubin $\leq 3.0\text{ mg/dL}$, AST and ALT < 2.5 times upper limit of normal
- H. No other active malignancies within the past 3 years (with the exception of non-melanoma skin cancers or carcinoma in situ of the bladder) or life threatening illnesses.
- I. Willing to travel to the NIH for follow-up visits.
- J. 18 years of age or greater.
- K. Able to understand and sign informed consent.
- L. Must agree to use effective birth control (such as a condom) or abstinence during and for a period of 4 months after the last vaccination therapy. Patients must be willing to remain on chemical castration therapy, unless they have had surgical castration.
- M. Patients must have recovered from acute toxicities related to prior therapy or surgery.

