3 STUDY IMPLEMENTATION

3.1 Study Design (see Schema)

This randomized Phase II study proposes to evaluate the role of second line antiandrogen therapy and a pox vector based PSA vaccine in a population of patients with prostate cancer who have a rising serum PSA despite castrate levels of testosterone and prior antiandrogen therapy but no metastatic disease on bone or CT scans. Patients will be randomized on a 1:1 basis to Arm A (flutamide alone) or Arm B (flutamide + vaccine).

Arm A: Flutamide 250 mg orally TID beginning on day 1.

Arm B: Flutamide 250 mg orally TID beginning on day 1.

PROSTVAC-V/TRICOM (vaccinia) 2×10^8 pfu subcutaneously on day 1 of the first cycle only, followed by monthly (every 4 week) boosting vaccinations with PROSTVAC-F/TRICOM (fowlpox) 1×10^9 pfu subcutaneously on day 1 of each cycle. The duration of each treatment cycle is approximately 28 days.

[figure not shown]
Patients may continue on the therapy they were randomized to until the development of measurable disease on scans, rising serum PSA, or if they develop toxicity requiring stopping of their treatment. For patients with declining PSA no restaging will be done unless they develop symptoms consistent with metastatic disease. For patients with rising PSA, once 2 consecutive

PSA rises are seen from the last imaging studies, CT and bone scans will be done at their next scheduled visit. They will then be re-staged (CT and bone scans) at 3 month intervals as long as PSA continues to rise.

1. Patients on either arm who develop clinical progression (i.e. evidence of metastatic disease on scans) will be taken off study.
2. Patients who do not develop clinical progression (as defined above), but develop biochemical recurrence (i.e rising serum PSA levels) will undergo the following:
 - After 3 months of therapy, patients randomized to the flutamide alone (arm A) may cross over to receive vaccine if they develop a rising PSA and scans are without metastatic disease. The vaccine may commence 4 weeks after flutamide is stopped (if the PSA continues to rise. If there is an antiandrogen withdrawal response (a decline in PSA 28 days after the discontinuation of flutamide), PSA serum levels will be checked every 28 days and vaccine may commence when the serum PSA levels begin to rise (if scans are negative for metastasis and if patients continue to meet the eligibility criteria as outlined in section 2.1).

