5.2.2 Biochemical Responses

5.2.2.1 PSA responses will be determined as below:

5.2.2.1.1 Complete response PSA < 0.2 confirmed by a second reading at least 4 weeks later.

5.2.2.1.2 PSA decline of > 50%.

All patients with a decline of PSA of at least 50% (confirmed by a second value at least 4 weeks after the first) and who have no other evidence of disease progression will be reported in this category. Patients will be reported with both PSA decline only and PSA decline and stable disease on scans.

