5.2.3 Duration of Overall Response (Biochemical Response)

5.2.3.1 The duration of overall response is measured from the time measurement criteria are met for CR or PR (whichever status is recorded first) until the first date that recurrence or PD is objectively documented.

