5.2.4 Reporting of Results

5.2.4.1 All patients included in the study must be assessed for response to treatment, even if there are major protocol treatment deviations or if they are ineligible. Each patient will be assigned one of the following categories: (1) complete response, (2) partial response, (3) stable disease, (4) progressive disease, (5) early death from malignant disease, (6) early death from toxicity, (7) early death because of other cause, or (8) unknown (not assessable, insufficient data).

5.2.4.2 All of the patients who met the eligibility criteria will be included in the main analysis of the response rate. Patients in response categories 4–9 will be considered as failing to respond to treatment (disease progression). Thus an incorrect treatment schedule or drug administration does not result in exclusion from the analysis of the response rate. Precise definitions for categories 4–9 will be protocol specific.

5.2.4.3 All conclusions should be based on all eligible patients.

5.2.4.4 Sub analyses may then be performed on the basis of a subset of patients, excluding those for whom major protocol deviations have been identified (e.g., early death due to other reasons, early discontinuation of treatment, major protocol deviations, etc.). However, these sub analyses may not serve as the basis for drawing conclusions concerning treatment efficacy, and the reasons for excluding patients from the analysis should be clearly reported.

5.2.4.5 The 95% confidence intervals should be provided.

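### The response rate for secondary objective 5 is tied to RECIST categories in men without metastatic disease on scans, and the plan never makes its PSA response criteria the rate to be analysed

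*Combined protocol and SAP*

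**What the plan says.** Secondary objective 5 (section 1.1.2) is "assessing response rate in patients randomized to both arms, as well as responses in those patients after cross over". It names no response criterion. Objective 4 in the same section refers separately to PSA responses after flutamide is stopped.

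Inclusion criterion B (section 2.1.1) requires "no evidence of metastatic disease on CT scan or bone scan". Section 6.5 describes the population as having no measurable disease on scans.

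On how response is judged, the plan says several things:

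- **Section 5.2.1, body text:** each patient receives one of five categories (complete response, partial response, stable disease, progressive disease, not evaluable), and "This protocol will use CTEP's Response Evaluation Criteria on Solid Tumors (RECIST) for assessing response".
- **Section 5.2.1, opening note:** new lesions by RECIST serve to define progression.
- **Section 5.2.1.3:** PSA is to be used to measure response as well as progression.
- **Section 5.2.2.1:** a PSA complete response is a value below 0.2 confirmed at least 4 weeks later. A second category is a decline of at least 50%, confirmed at least 4 weeks later, with no other evidence of progression. For that category, "Patients will be reported with both PSA decline only and PSA decline and stable disease on scans".
- **Section 5.2.3.1**, under a heading that specifies biochemical response: duration is "measured from the time measurement criteria are met for CR or PR (whichever status is recorded first".
- **Section 5.2.4:** eight categories are listed, again starting with complete response, partial response and stable disease. All eligible patients enter the main response-rate analysis, and "Patients in response categories 4–9 will be considered as failing to respond to treatment (disease progression".

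**The concern.** A RECIST complete or partial response needs a lesion that can disappear or shrink. Men admitted under criterion B have no metastatic lesion at baseline. If the body text of 5.2.1 is carried through to 5.2.4.2, the response rate sits near zero in each arm and after crossover, whatever the treatments do. The outcome that can differ between arms, a confirmed PSA decline, is defined but is not named as the quantity analysed.

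An analyst could therefore report three different response rates from the same data: RECIST, PSA below 0.2 only, or a confirmed decline of at least 50%. If the choice is made after the data are seen, the comparison for objective 5 is hard to interpret.

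**Working it through.** **Figures in the plan.** The plan states no expected response rate, so there is none to reproduce. The 31 per arm used below is the post-amendment-F sample size for time to treatment failure (section 5.4). It does reproduce:

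- Inputs: hazards 0.0693 and 0.0385 per month, accrual A = 60 months, further follow-up F = 24 months, one-sided alpha 0.10, power 80%, hazard ratio 1.80.
- Event probability with uniform accrual: 1 − [exp(−λF) − exp(−λ(A+F))]/(λA), giving 0.955 and 0.845.
- Expected events: 31 × (0.955 + 0.845) = 55.8.
- Freedman's formula needs 56 events (31.1 per arm). Schoenfeld's needs 53 (29.4 per arm).

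Nothing in this calculation depends on the response rate.

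**RECIST reading.** Assume no eligible man has a lesion that can respond. The estimate is then 0/31 in each arm. The exact (Clopper-Pearson) two-sided 95% upper limit for 0/n is 1 − 0.025^(1/n):

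- n = 31: 1 − 0.025^(1/31) = 11.2%.
- n = 62: 1 − 0.025^(1/62) = 5.8%.

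Both arms give the same interval, so no difference can be seen.

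**PSA reading.** Under 5.2.2.1 a man without lesions can meet either PSA criterion, so the rate is not forced to zero. The documents give no expected PSA response rate, so no corrected figure can be calculated. The two PSA criteria are nested on the PSA scale. Criterion B requires a last PSA above 1 ng/ml, so a fall from above 1 to below 0.2 is a decline of more than 1 − 0.2/1 = 80%, which exceeds 50%. This takes the PSA from which decline is measured to be above 1 ng/ml as well.

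**Which reading the text selects.**

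- For RECIST: the sentence in 5.2.1; the reference in 5.2.1.1 to target lesions chosen for response assessment; the RECIST measurements required in the database in section 5.5; and the 5.2.4.1 list, which contains no PSA category.
- For PSA: the note opening 5.2.1, section 5.2.1.3, and the heading of 5.2.3.
- Undecided: objective 5 names no criterion, 5.2.4 names neither RECIST nor PSA, and section 5.4 lists only four secondary objectives and gives no response-rate analysis.

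**Duration.** Section 5.2.3.1 starts the clock at complete or partial response. Section 5.2.2.1 labels PSA below 0.2 a complete response but attaches no partial-response label to the 50% decline. Only the former has an explicit start date.

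**Numbering.** Section 5.2.4.2 refers to categories 4 to 9; 5.2.4.1 lists eight and 5.2.1 lists five. Stable disease (category 3) is not classed as failure and is not a response.

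**Scan split.** All patients are scanned at week 12 (section 3.1). After that, "For patients with declining PSA no restaging will be done unless they develop symptoms consistent with metastatic disease". A man whose PSA is still falling and who has no symptoms therefore has no later scan from which to call stable disease.

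**The case against.** The strongest reply is that the authors saw the mismatch and dealt with it. The note opening 5.2.1 recalls that patients must be non-metastatic and gives RECIST the role of defining progression; 5.2.1.3 makes PSA a response measure; 5.2.2.1 defines it; and 5.2.3 is headed as biochemical response. On that view the RECIST sentence is leftover generic text. The missing partial-response label has an obvious candidate, because the 50% decline is the only other PSA response category. The numbering slip changes no result, since no ninth category exists and stable disease would not enter a response numerator in any case.

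Much of this stands. A reader might infer that the response rate and its duration are zero or undefined by construction. The documents do not support that: a PSA rate can be computed, and a PSA complete response has an explicit start date. A reader might also infer that the scan split is never available after week 12. That goes too far, because men whose PSA later rises twice, or who develop symptoms, are scanned.

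What the reply does not show is that the PSA rate is the one 5.2.4.2 analyses. No section says so, and objective 4 names PSA responses where objective 5 says only response rate.

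**Conclusion.** The concern holds as a conflict between response rules. The rule stated in 5.2.1 and carried into 5.2.4.2 would give an essentially 0% response rate in both arms (0/31, upper limit 11.2%) and no information on treatment. The usable PSA definitions are present but are not designated as the analysed rate, and the start of response duration is explicit only for PSA below 0.2.

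The 0/31 figure rests on the RECIST-only reading and on no eligible man having a lesion that can respond. Criterion B excludes metastatic disease and does not expressly exclude every local finding, hence essentially rather than exactly zero. The numbering and the scan split are minor.

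The conflict should be resolved, but it touches a secondary objective only. It would be wrong to read it as weakening the primary comparison: time to treatment failure and its sample size are unchanged.

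**What to change.** - **5.2.1:** limit RECIST to detecting new lesions, that is, progression, in line with the section's own opening note.
- **5.2.4.2:** define the response rate as the proportion of eligible patients with a confirmed PSA decline of at least 50% and no other progression. Report confirmed PSA below 0.2 as the complete-response subset. Count all other patients as non-responders, and replace the reference to categories 4 to 9.
- **5.2.3.1:** time duration from the first qualifying PSA value to PSA progression or metastasis.
- **5.2.2.1.2:** limit the stable-disease-on-scans split to patients with a scan at the relevant time, generally week 12.
- **5.4:** as a conforming edit, add objective 5 and its analysis, with the 95% confidence intervals that 5.2.4.5 already asks for.

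The cost is wording in these sections. No new data are needed, because serial PSA is already collected. The reference PSA for declines after crossover could be stated at the same time, but that is a refinement and this point does not depend on it.

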5.2.2 Biochemical Responses

5.2.2.1 PSA responses will be determined as below:

5.2.2.1.1 Complete response PSA < 0.2 confirmed by a second reading at least 4 weeks later.

5.2.2.1.2 PSA decline of > 50%.

All patients with a decline of PSA of at least 50% (confirmed by a second value at least 4 weeks after the first) and who have no other evidence of disease progression will be reported in this category. Patients will be reported with both PSA decline only and PSA decline and stable disease on scans.

5.2.2.2 Time to PSA Progression

In the absence of evidence of clinical progression on scans, we believe that time to PSA progression may also be an important variable to report. In this trial, PSA progression will be evaluated based on the PSA level at the time treatment is initiated compared to the PSA level at week 12 and monthly thereafter while the patient continues on trial. If

at least a 50% decline in PSA has been achieved, the end date is the time that the PSA has increased 50% above the nadir and a minimum of 5ng/ml. For patients without a PSA fall of this magnitude (or no fall in PSA), the endpoint for progression will be calculated at a time a 25% increase in PSA over nadir has been achieved with a minimum increase of 5 ng/ml. (see section **5.2.1.3**)

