5.4 Statistical Considerations

The primary objective of this randomized trial is to determine if use of a combination of vaccine plus flutamide may be associated with a trend toward improvement in time to treatment failure in patients with stage D0.5 prostate cancer compared to that which would occur with flutamide alone.

Secondary objectives are 1) determining preliminary evidence of any patterns of immunologic effects which differ by treatment including the immunologic effects of flutamide withdrawal on patients continuing on vaccine following a rising PSA on flutamide, 2) estimating toxicity noted on the arms and comparing the results, 3) evaluating, in a preliminary fashion, the effect of vaccine on development of metastatic disease after PSA progression, and 4) evaluating PSA responses and immune responses in patients who have had flutamide stopped at the time of PSA progression and either continue vaccine (Arm B) or have vaccine initiated (arm A) at time of flutamide discontinuation

The trial will be conducted as a randomized pilot trial with two arms as follows:

Arm A: flutamide

Arm B: flutamide + vaccine

Patients will be stratified based on a projected PSA doubling time (PSADT) of > 10 months vs. ≤ 10 months using the last 2 PSA values 1 month apart prior to enrollment on study.

$$\text{PSADT} = \frac{\log(2) \times t}{\log(\text{final PSA}) - \log(\text{initial PSA})}$$

t=time from initial to final PSA determination

$$\log(2) = 0.301$$

Time to treatment failure (TTF) will be the primary endpoint of this trial, where a treatment failure would be defined as a rising PSA (Bublely Criteria, JCO, 1999), development of metastatic disease, or removal from treatment due to excessive toxicity. Because PSA will be measured monthly and metastatic disease will be evaluated every 3 months, this will be sufficiently frequent for the primary evaluation to be made using standard actuarial methods (Kaplan-Meier plots with a log-rank p-value determinations).

The previously published trial of Nilutamide in a similarly eligible population of patients (stage

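### Time to PSA failure depends strongly on starting PSA because of the 5 ng/ml minimum rise, and the primary log-rank test takes no account of baseline PSA

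*Combined protocol and SAP*

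**What the plan says.** - **Entry.** Section 2.1.1, criterion B, requires two consecutive rises "separated by at least 1 month apart, with the last measurement that is" above 1 ng/ml. No higher floor is given.
- **PSA rule, no 50% fall.** Section 5.2.2.2 sets progression at the time "a 25% increase in PSA over nadir has been achieved with a minimum increase of 5 ng/ml".
- **PSA rule after a fall of at least 50%.** "the end date is the time that the PSA has increased 50% above the nadir and a minimum of 5ng/ml".
- **Timing.** PSA at treatment start is "compared to the PSA level at week 12 and monthly thereafter while the patient continues on trial".
- **Link to failure.** Section 5.2.1.3 directs the change of treatment "if a patient has a rising serum PSA level (see section 5.2.2.2) but no evidence of metastatic disease", which sends the reader to the numeric rule. Section 5.4 states that "Time to treatment failure (TTF) will be the primary endpoint of this trial" and counts a rising PSA as failure. It cites a published criterion there without restating it.
- **Analysis.** Section 5.4 plans the "primary evaluation to be made using standard actuarial methods (Kaplan-Meier plots with a log-rank p-value determinations"). It names no covariate and no stratified test.
- **Randomisation strata.** These are projected PSA doubling time (cut at 10 months) and, after amendment F, combined androgen therapy status. Baseline PSA level is not among them, although Sections 2.2 and 3.4.3 require it for every patient.

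**The concern.** A rule that combines a percentage with an absolute minimum treats low and high starting values differently. Two men whose PSA doubles at the same rate can be declared failures many months apart only because one entered at 1.5 ng/ml and the other at 20 ng/ml.

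If PSA failure supplies most of the events, much of the variation in the primary endpoint then comes from a quantity that is known before randomisation and has nothing to do with treatment. A test that ignores it gives up power. With 31 patients per arm, a chance difference in baseline PSA can also move the estimated effect noticeably in either direction.

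**Working it through.** **1. The plan's own sample size.** Inputs from Section 5.4 after amendment F: medians 10.0 and 18.0 months, hazard ratio 1.80, one-sided alpha 0.10, power 80%, accrual A = 60 months, further follow-up F = 24 months. For exponential hazard λ the event probability is 1 − [exp(−λF) − exp(−λ(A+F))]/(λA).
- λ = 0.0693 gives 0.955; λ = 0.0385 gives 0.845; sum 1.800.
- Freedman events: (2.80/0.80)² × (1.2816 + 0.8416)² = 12.25 × 4.508 = 55.2, so 56. Per arm: 56/1.800 = 31.1.
- Schoenfeld: 53 events, 29.4 per arm.

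The stated 31 per arm reproduces. The sample size is not in question.

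**2. Where the 5 ng/ml minimum decides.** 25% of the nadir equals 5 ng/ml when the nadir is 5/0.25 = 20 ng/ml. Below 20 the absolute minimum governs.

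**3. Time to PSA failure at a fixed doubling time.** With exponential growth and no fall, so that the nadir is the starting value P0:

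time = doubling time × log2(max(1.25, 1 + 5/P0))

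| P0 (ng/ml) | Fold rise needed | Doublings | Months, 6-month doubling | Months, 10-month doubling |
|---|---|---|---|---|
| 1.5 | 4.33 | 2.115 | 12.7 | 21.2 |
| 2 | 3.50 | 1.807 | 10.8 | 18.1 |
| 5 | 2.00 | 1.000 | 6.0 | 10.0 |
| 10 | 1.50 | 0.585 | 3.5 | 5.8 |
| 20 or more | 1.25 | 0.322 | 1.9 | 3.2 |

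The first comparison is at week 12, which is 84/30.4 = 2.76 months, so the 1.9 cannot be observed and becomes about 2.8. At a 6-month doubling time the observable spread is 12.69/2.76 = 4.6-fold, a gap of about 10 months. The planned difference in medians is 8 months. Each column holds the doubling time fixed, so stratifying on doubling time leaves the spread in place.

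**4. Effect on power.** The documents give no baseline PSA distribution, so every input here is an assumption. Scenario without PSA falls: 31 per arm; log-normal baseline PSA (log-SD 1, truncated at 1 ng/ml); doubling time median 10 months, log-SD 0.7; vaccine multiplies doubling time by 1.8; other failures 0.01 per month; monthly assessment from month 3; the plan's accrual and follow-up; 1,000 runs. Strata for the second test are <5, 5 to <20 and ≥20 ng/ml.

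| Median baseline PSA | Plain log-rank | Stratified log-rank | Gain (points) |
|---|---|---|---|
| 5 | 0.770 | 0.855 | 8.5 |
| 10 | 0.755 | 0.884 | 12.9 |
| 20 | 0.818 | 0.888 | 7.0 |

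With no treatment effect the plain test rejected in 10.2 to 10.7% of runs and the stratified test in 9.7 to 11.1%, so both hold the 10% level within simulation error.

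Scenarios with PSA falls on flutamide (assumed nadir 10 to 100% of baseline, other failures 0.01 to 0.03 per month, 1.8-fold effect, 300 runs each) gave gains of about 3 to 8 points. One of these reproduced medians of about 10 and 17 months; there plain power was 0.91 to 0.93 and the gain 3 to 4 points. A further set at 1.8-fold gave about 80 to 92% plain and 84 to 95% stratified, a gain of 3 to 11 points.

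**5. Chance imbalance.** In the scenario without falls, the share of men below 5 ng/ml differed between arms by at least 10 percentage points in 28 to 39% of runs (median 5 or 10 ng/ml) and in 8 to 11% (median 20). In a separate set of null runs (doubling time median 6 months, baseline median 5, 8 or 20), the log-rank Z correlated 0.43 to 0.57 with the imbalance in mean log baseline PSA. That is 0.43² = 0.18 to 0.57² = 0.32 of its null variance.

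**The case against.** The plan contains no error of validity. Under 1:1 randomisation the unadjusted log-rank test is sound, and a chance imbalance that looks like benefit is already inside the one-sided 10% error rate. A reader might infer from the table that the comparison is biased or that false positives are inflated; the design and the null simulations do not support that. This part of the objection stands in full.

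Three other strong readings also fail.
- **A nearly 7-fold spread at a 6-month doubling time** (12.7/1.9) ignores the week-12 first comparison; 4.6-fold is the observable figure.
- **Power well below 80%.** Plain log-rank power of roughly 54 to 69% appears only if the vaccine effect is set at 1.5-fold. The plan targets 10 against 18 months, a ratio of 1.8. Its original 7.6-month control median came from a similar population under the same failure definition, so that figure already carried some spread in baseline PSA.
- **Failure fixed by baseline PSA alone.** The rule runs from the nadir, so after a fall on flutamide baseline is only a proxy. Metastasis and removal for toxicity also count as failure and dilute the dependence.

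Two further points deserve weight. Time to treatment failure reaches the numeric rule only through the cross-reference in 5.2.1.3, because 5.4 cites the published criterion alone. And a log-linear baseline PSA term would fit poorly, since dependence is flat above 20 ng/ml; a stratified test avoids that. What survives is the loss of efficiency: the gain stayed positive across the scenarios examined at a 1.8-fold effect, and the covariate is already collected.

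**Conclusion.** The point holds as one of efficiency and robustness, not of bias. The 5 ng/ml minimum governs PSA failure for every patient without a 50% fall whose nadir is below 20 ng/ml, and neither the strata nor the planned test accounts for starting PSA. At a 6-month doubling time with no fall, the resulting spread is about 4.6-fold.

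Under assumed baseline medians of 5 to 20 ng/ml and a 1.8-fold effect, accounting for baseline PSA is worth about 3 to 13 points of power. Gains are generally smaller if PSA falls on flutamide are common.

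The conclusion rests on three things: the link from rising PSA to 5.2.2.2 through 5.2.1.3; exponential PSA growth in the worked times; and a meaningful share of men with nadirs below 20 ng/ml, which the documents do not report. For men with a fall of at least 50%, the size of the dependence also turns on whether the 5 ng/ml in that clause is an increase or a level. From a nadir of 1 ng/ml these need log2(6) = 2.58 or log2(5) = 2.32 doublings.

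**What to change.** Leave the endpoint definition and patient management as they are. In Section 5.4, before the treatment comparison is made:

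1. Specify that the log-rank test of time to treatment failure, at one-sided 0.10, is stratified by baseline PSA category, for example <5, 5 to <20 and ≥20 ng/ml.
2. Include baseline PSA, together with the randomisation strata, in the Cox model that estimates the hazard ratio. Using the same categories avoids a log-linear term that the rule does not follow above 20 ng/ml.
3. Report the unadjusted log-rank test as a sensitivity analysis.
4. Tabulate baseline PSA by arm.

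The cost is a little more analysis work and some small strata with 62 patients. No new data are needed. Because treatment assignment is known in this trial, the change should be dated and made without reference to outcomes by arm. If the comparison has already been made, the stratified result should be labelled supportive.
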